## 8.3 ADVERSE EVENTS AND SERIOUS ADVERSE EVENTS

### 8.3.1 DEFINITION OF ADVERSE EVENTS

An AE is any untoward medical occurrence in a patient or clinical investigation patient administered a pharmaceutical product and that does not necessarily have a causal relationship with this treatment. An AE can therefore be any unfavorable and unintended sign (including an abnormal laboratory finding), symptom, or disease temporally associated with the use of a medicinal (investigational) product, whether or not related to that product. Worsening of the pterygium is not an AE, unless the lesion growth is greater than expected.

Treatment-emergent AEs are any AEs with an onset date equal to or after the date of the first insertion of the study lens and during the treatment. A pre-existing event that worsens after the first treatment date is considered a treatment-emergent event.

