### 8.2 SAFETY AND OTHER ASSESSMENTS

Abnormal findings that are of clinical significance will be recorded as AEs on the eCRFs.

- **Ultrasound pachymetry.** Corneal thickness will be measured using an ultrasound pachymeter.
- **Humphrey visual field assessment.** Visual field (perimetry) will be assessed using a Humphrey Field Analyzer. If Humphrey visual field assessment has been completed within 6 months of Screening Visit, it does not have to be repeated at the Screening Visit
- **Contact Lens (CL) Assessment:** Assessments will include contact lens centration, movement with blinking, and lens surface wettability/deposits, as described in ISO 11980:2012.
- **Heart rate and blood pressure.** Heart rate and blood pressure will be measured by a manual or automated sphygmomanometer.
- **Pregnancy testing.** Pregnancy testing will be performed using a human chorionic gonadotropin pregnancy urine dipstick test on women of childbearing potential.
- **Best-corrected visual acuity.** BCVA will be quantified using the ETDRS visual acuity protocol (at a distance of 3 m) and the number of letters read correctly will be recorded on the eCRF.
- **Biomicroscopy.** Biomicroscopy will be performed by slit-lamp examination of conjunctiva, cornea, and iris with findings reported on a scale of 0 = none, 0.5 = trace, 1 = mild, 2 = moderate, and 3 = severe. The status of the lens will be assessed using the Age-Related Eye Disease Study scale.
- **Goldmann applanation tonometry.** IOP will be measured with a Goldmann applanation tonometer. During the study, the LL-BMT1 contact lens will be removed in order to perform IOP assessment. Of particular significance, all lens insertions and removals will be conducted by the investigator. IOP will be assessed 3 minutes after lens removal, with the goal of reinserting the lens within 5 minutes of removal. Two consecutive IOP measurements of each eye were obtained. If the 2 measurements differed by more than 2 mmHg, a third measurement was obtained. For each eye, IOP was analyzed as the mean

of 2 measurements or as the median of 3 measurements. For each patient, change from baseline IOP was determined by averaging the values for each eye (Sherwood 2006).

- **Conjunctival hyperemia.** The Efron Grading Scales for Contact Lens Complications will be performed using a conjunctival hyperemia scale.

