#### 8.3.4 TIME PERIOD AND FREQUENCY FOR EVENT ASSESSMENT AND FOLLOW-UP

Any medical condition that is present at the time that the patient is screened will be considered as medical history and not reported as an AE. However, if the study patient’s condition deteriorates at any time after enrollment, it will be recorded as an AE.

Changes in the severity of an AE will be documented to allow an assessment of the duration of the event at each level of severity to be performed. AEs characterized as intermittent require documentation of onset and duration of each episode.

The investigator or qualified designee will record all reportable events with start dates occurring any time after informed consent is obtained until 7 days (for non-serious AEs) or 30 days (for SAEs) after the last day of study participation. Patient will be told to call and notify the investigator of such events that occur during this period after the end of study visit. Events will be followed for outcome information until resolution or stabilization.

AEs will be monitored throughout the study beginning at the time the patient signs the informed consent for this study. At each post-Baseline visit, the investigator will begin by querying for AEs by asking each patient a general, non-directed question, such as “How have you been feeling since the last visit?” Directed questioning and examination will then be done as appropriate. All reported AEs will be documented on the appropriate eCRF, including seriousness, severity, relationship to study drug, action taken, and outcome (including date of resolution or stabilization, if AE is not ongoing). If AEs occur, the first concern will be the safety of the study patients.

If a patient becomes pregnant during the study, the investigator must inform the Sponsor and collect follow-up data regarding the pregnancy, birth, and status of the child. The Sponsor will provide special CRFs for data collection in the case of pregnancy. Follow-up should be continued until study close-out at the study center. After close-out, the Sponsor's Safety designee will continue to obtain follow-up information. Pregnancy should be recorded as a protocol deviation. Pregnancy is not an AE; however, any complication related to pregnancy would be considered an AE.

---

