### 9.4.2 SAFETY ANALYSES

Analysis of treatment-emergent AEs will be conducted based on the safety population. Safety endpoints include:

- AEs
- Concomitant medications
- Heart rate and blood pressure
- BCVA
- IOP
- Biomicroscopy
- Conjunctival hyperemia

Ocular events will be reported on an eye level, while non-ocular events will be on a patient level.

AEs will be coded using the Medical Dictionary for Regulatory Activities (MedDRA). For each AE reported, the number and percent of patients/eyes will be tabulated based on the preferred term and ocular and non-ocular AEs will be reported separately. The tables will be generated by relationship to treatment as well as by system organ class and severity.

The primary safety endpoint is the AE rate ( $100 \times [\text{number of AEs} / \text{number of eyes exposed to treatment}]$ ). The modified safety set will be used for a sensitivity analysis of the primary safety endpoint.

*Secondary safety endpoints:*

- Percent of patients with  $\geq 5$ -mmHg increase from baseline in IOP at each visit
- Abnormal slit-lamp biomicroscopy findings at the Baseline, Day 1, and Day 7 Visits
- Contact lens protein deposits at the Day 7 Visit
- Change from baseline in CLDEQ-8 results at the Day 7 Visit

Pre-existing AEs, those identified after enrollment but before treatment with LL-BMT1, will be tabulated for all consented patients.

---

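### Protocol 8.3.1 exempts pterygium worsening from being an AE unless growth exceeds an undefined expectation; this is unreconciled with 8.3.4 and 8.2 and can only lower the primary AE count

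*Protocol*

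**What the plan says.** Protocol 8.3.1 opens with the usual broad definition: any unfavorable sign, symptom or disease counts, "whether or not related to that product". The same paragraph then ends with an exemption: "Worsening of the pterygium is not an AE, unless the lesion growth is greater than expected". The next paragraph defines treatment-emergent events and adds: "A pre-existing event that worsens after the first treatment date is considered a treatment-emergent event".

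Two other sections also decide what is recorded. Protocol 8.3.4 treats conditions present at screening as medical history, but adds that "if the study patient’s condition deteriorates at any time after enrollment, it will be recorded as an AE". Protocol 8.2 says: "Abnormal findings that are of clinical significance will be recorded as AEs on the eCRFs". It also says what the eye examination covers: "Biomicroscopy will be performed by slit-lamp examination of conjunctiva, cornea, and iris".

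Protocol 9.4.2 states: "The primary safety endpoint is the AE rate", calculated as 100 times the number of AEs divided by the number of exposed eyes. SAP 5.1 and 6.7 use the same rate, and SAP 6.7 bases the primary analysis on treatment-emergent AEs. The SAP does not say what an AE is, and SAP 1.1 declares no changes from the protocol, so the definition in 8.3.1 carries over, exemption included.

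**The concern.** A rule on what counts as an AE is part of the definition of the primary endpoint. This one singles out a lesion that the trial population is not required to have, in a study of an ocular-surface device. It gives no reason for doing so, and its exception depends on an expected growth that is never stated.

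An investigator who sees a pterygium worsen would therefore get different answers from different sections on whether to record it. At up to two sites and with five patients, the choice would be made case by case. Whenever 8.3.1 is followed, the event drops out of the primary count.

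**Working it through.** **1. Where pterygium appears.** Only in this one sentence of 8.3.1. The disease under study is open-angle glaucoma or ocular hypertension in both eyes (Protocol 5.1, criterion 2). The nearest exclusion is criterion 12 in Protocol 5.2, which covers corneal pathology that the investigator considers a contraindication to lens wear. A patient with a pterygium can therefore be enrolled unless that judgment, or the general discretion in criterion 26, goes against it.

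**2. The rules side by side.** Take a pterygium present at screening that worsens after the first LL-BMT1 insertion, with growth not judged beyond expectation.

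| Rule | Result for this event |
|---|---|
| 8.3.1, exemption | Not an AE |
| 8.3.4, deterioration after enrollment | AE |
| 8.2, abnormal findings | AE if clinically significant |
| 8.3.1, second paragraph | Treatment-emergent, if it counts as an event at all |

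The first row conflicts with the second, and with the third when the finding is clinically significant. The fourth row is weaker evidence. That rule classifies the timing of events and speaks of a pre-existing event, so it fits awkwardly with the exemption rather than contradicting it outright. Neither 8.3.4 nor 8.2 mentions an exception.

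**3. Whether the exception can be applied.** It needs a baseline lesion size and an expected growth over the period. The schedule of activities has no lesion measurement, the slit-lamp grading in 8.2 is a general severity scale, and no expected growth is given. Treatment lasts one week.

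**4. Direction and size.** The sentence only removes events, so it cannot raise the rate. The documents state no AE rate to reproduce; the size follows from the endpoint formula.

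- Planned eyes: 5 patients (Protocol 9.2) × 2 treated eyes (Protocol 4.1) = 10.
- One uncounted event: 100 × 1/10 = 10 per 100 eyes.
- Two uncounted events: 100 × 2/10 = 20 per 100 eyes.
- One uncounted event if only 9 eyes were exposed: 100 × 1/9 = 11.1 per 100 eyes.

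**5. How often it could arise.** The documents give no prevalence of pterygium, so the figures below rest on assumed values p and on independence between patients. The chance that at least one of five patients has a pterygium is 1 − (1 − p)^5:

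| Assumed p | Chance of at least one in five |
|---|---|
| 1% | 4.9% |
| 5% | 22.6% |
| 10% | 41.0% |
| 15% | 55.6% |

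These are chances of having the lesion, before any exclusion. The chance that it also worsens during the week, without growth judged beyond expectation, is smaller, and the documents give no figure for it.

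**The case against.** The strongest reply is that a specific exception normally prevails over a general rule, so 8.3.1 could be read as deliberately narrowing 8.3.4. That reading is possible, but it needs a stated reason and a usable criterion, and the protocol gives neither.

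A second reply is that patients whose eyes react to lens wear should be removed in the two-week run-in: inclusion criterion 7 requires no adverse reactions to the nonmedicated lenses, and Protocol 4.1 requires no lens-related AEs. This does narrow the scenario. However, the 4.1 condition is itself worded in terms of AEs, so the exemption reaches it too; criterion 7 and investigator discretion are the firmer filters.

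A third reply is that surface changes would show elsewhere. Biomicroscopy and conjunctival hyperemia are safety endpoints in Protocol 9.4.2 and SAP 5.2, and Protocol 9.4.7 provides line listings for each patient. This stands. With five patients, a worsening lesion would probably be seen in those data even if it were missing from the AE rate.

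A reader might infer that the sentence takes inflammation, irritation or redness around a pterygium out of the AE count. The text does not support that. It names worsening of the lesion, and the only criterion it gives is growth. Separate signs and symptoms can still be recorded under the general definition in 8.3.1 and under 8.2. A reader might also take all pterygium worsening to be exempt, but growth beyond expectation remains an AE, however poorly that is defined.

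**Conclusion.** The concern holds as an unreconciled exemption inside the definition of the primary endpoint. It conflicts with 8.3.4, and with 8.2 for clinically significant findings; against the treatment-emergent rule in 8.3.1 it is awkward rather than contradictory. Its effect on the AE rate can only be downward: 10 per 100 eyes for each uncounted event, assuming all 10 planned eyes are exposed.

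In practice the effect is probably small. It needs an enrolled patient with a pterygium, worsening within one week of wear, and growth not judged beyond expectation. The analysis is descriptive and no hypothesis is tested, so no decision threshold depends on the count. This is a minor correction.

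Because the sentence speaks as though every patient had the lesion, a reader might infer that it was carried over from a protocol for another disease. That is plausible, but the documents do not say so, and the point does not depend on it.

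**What to change.** Delete the sentence on pterygium from Protocol 8.3.1. The general AE definition, the deterioration rule in 8.3.4 and the findings rule in 8.2 then apply alike to all pre-existing ocular conditions. The SAP does not repeat the sentence and needs no change on this point.

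The cost is one deleted sentence in an amendment, which the protocol's compliance statement sends through IRB review. Sample size, visits, procedures and analysis methods are unaffected.

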### 8.3.2 DEFINITION OF SERIOUS ADVERSE EVENTS

An SAE is any AE occurring at any dose that results in any of the following outcomes: death, a life-threatening AE, inpatient hospitalization or prolongation of existing hospitalization, a persistent or significant disability/incapacity, or a congenital anomaly/birth defect. Important medical events that may not result in death, be life-threatening, or require hospitalization may be considered an SAE when, based upon appropriate medical judgment, they may jeopardize the patient and may require medical or surgical intervention to prevent one of the outcomes listed in this definition. See Section 8.3.6 for procedures for reporting an SAE.

### 8.3.3 CLASSIFICATION OF AN ADVERSE EVENT

#### 8.3.3.1 SEVERITY OF EVENT

For AEs not included in the protocol-defined grading system, the following guidelines will be used to describe severity.

- **Mild:** Event requires minimal or no treatment and do not interfere with the patient's daily activities
- **Moderate:** Event results in a low level of inconvenience or concern with the therapeutic measures. Moderate events may cause some interference with functioning

- **Severe:** Event interrupts a patient’s usual daily activity and may require systemic drug therapy or other treatment. Severe events are usually potentially life-threatening or incapacitating. Of note, the term “severe” does not necessarily equate to “serious”

---

#### 8.3.3.2 RELATIONSHIP TO STUDY INTERVENTION

A determination will be made of the relationship (if any) between an AE and the study drug. A causal relationship is present if a determination is made that there is a reasonable possibility that the AE may have been caused by the drug and/or the lens.

- **Unrelated:** A causal relationship can be excluded and another documented cause of the AE is most plausible
- **Unlikely related:** A causal relationship is improbable, and another documented cause of the AE is most plausible
- **Possibly related:** A causal relationship is clinically/biologically plausible and there is a plausible time sequence between onset of the AE and administration of the study drug
- **Probably related:** A causal relationship is clinically/biologically highly plausible, there is a plausible time sequence between onset of the AE and administration of the study drug, and there is a reasonable response on withdrawal

---

#### 8.3.4 TIME PERIOD AND FREQUENCY FOR EVENT ASSESSMENT AND FOLLOW-UP

Any medical condition that is present at the time that the patient is screened will be considered as medical history and not reported as an AE. However, if the study patient’s condition deteriorates at any time after enrollment, it will be recorded as an AE.

Changes in the severity of an AE will be documented to allow an assessment of the duration of the event at each level of severity to be performed. AEs characterized as intermittent require documentation of onset and duration of each episode.

The investigator or qualified designee will record all reportable events with start dates occurring any time after informed consent is obtained until 7 days (for non-serious AEs) or 30 days (for SAEs) after the last day of study participation. Patient will be told to call and notify the investigator of such events that occur during this period after the end of study visit. Events will be followed for outcome information until resolution or stabilization.

AEs will be monitored throughout the study beginning at the time the patient signs the informed consent for this study. At each post-Baseline visit, the investigator will begin by querying for AEs by asking each patient a general, non-directed question, such as “How have you been feeling since the last visit?” Directed questioning and examination will then be done as appropriate. All reported AEs will be documented on the appropriate eCRF, including seriousness, severity, relationship to study drug, action taken, and outcome (including date of resolution or stabilization, if AE is not ongoing). If AEs occur, the first concern will be the safety of the study patients.

If a patient becomes pregnant during the study, the investigator must inform the Sponsor and collect follow-up data regarding the pregnancy, birth, and status of the child. The Sponsor will provide special CRFs for data collection in the case of pregnancy. Follow-up should be continued until study close-out at the study center. After close-out, the Sponsor's Safety designee will continue to obtain follow-up information. Pregnancy should be recorded as a protocol deviation. Pregnancy is not an AE; however, any complication related to pregnancy would be considered an AE.

---

### 8.3.5 ADVERSE EVENT REPORTING

Any AE should be recorded on the appropriate eCRF.

---

### 8.3.6 SERIOUS ADVERSE EVENT REPORTING

Any SAE occurring during the study period should be immediately (ie, within 24 hours of learning of the event) reported to a Trial Runners representative listed on the protocol cover page. The SAE is recorded on the appropriate eCRFs. In the event of an early termination within 8 days after study drug administration, the occurrence of an SAE within 8 weeks from Baseline (Day 0) should be reported immediately to Trial Runners personnel. All patients with an SAE that is related to study drug must be followed for at least 30 days and the outcomes reported until the event is resolved or stabilized. The investigator should supply the Sponsor and the IRB with any additional requested information (e.g., autopsy reports and terminal medical reports).

In the event of an SAE, the investigator must:

- Notify the Trial Runners safety office and the medical monitor immediately by fax using the SAE reporting forms provided by Trial Runners (see first page of the protocol for the SAE fax number). Emergency phone numbers and relevant personnel contacts are below:
  - [REDACTED]
    - [REDACTED]
    - [REDACTED]
  - [REDACTED]
    - [REDACTED]
    - [REDACTED]
- Obtain and maintain in the patient's files all pertinent medical records, information, and medical judgments from colleagues who assisted in the treatment and follow-up of the patient
- Provide Leo Lens Technology with a complete, written case history (AE report form) which includes a statement as to whether the event was or was not related to the use of the investigational drug
- Promptly inform the governing IRB of the SAE if it is drug-related. For other SAEs, notify the governing IRB as required by the IRB, local regulations, and the governing health authorities

Adverse drug reactions that are both serious and unexpected (suspected unexpected serious adverse reactions) will be subject to expedited reported to the IRB as required by the relevant regulations. Reporting must occur within 15 calendar days of first knowledge, or for fatal or life-threatening events, an initial or full report must be made within 7 calendar days and a follow-up report must be made, if necessary, within the 15-calendar day timeframe.

---

#### 8.3.7 REPORTING EVENTS TO PATIENTS

Not applicable.

---

#### 8.3.8 EVENTS OF SPECIAL INTEREST

Not applicable.

---

#### 8.3.9 REPORTING OF PREGNANCY

If a female patient becomes pregnant during the study, the investigator will notify Trial Runners and the medical monitor immediately after the pregnancy is confirmed and the patient will be exited from the study. The investigator will (1) notify the patient's physician that the patient was being treated with LL-BMT1 or bimatoprost, as appropriate, and (2) follow the progress of the pregnancy to term on the patient providing written informed consent for release of this data. The investigator should document the outcome of the pregnancy and provide a copy of the documentation to Leo Lens Technology.

---

### 8.4 UNANTICIPATED PROBLEMS

---

#### 8.4.1 DEFINITION OF UNANTICIPATED PROBLEMS

The Office for Human Research Protections (OHRP) considers unanticipated problems involving risks to patients or others to include, in general, any incident, experience, or outcome that meets **all** of the following criteria:

- Unexpected in terms of nature, severity, or frequency given (a) the research procedures that are described in the protocol-related documents, such as the IRB-approved research protocol and informed consent document; and (b) the characteristics of the patient population being studied
- Related or possibly related to participation in the research (“possibly related” means there is a reasonable possibility that the incident, experience, or outcome may have been caused by the procedures involved in the research)
- Suggests that the research places patients or others at a greater risk of harm (including physical, psychological, economic, or social harm) than was previously known or recognized

This definition could include an unanticipated adverse device effect, any serious adverse effect on health or safety or any life-threatening problem or death caused by, or associated with, a device, if that effect, problem, or death was not previously identified in nature, severity, or degree of incidence in the investigational plan or application (including a supplementary plan or

application), or any other unanticipated serious problem associated with a device that relates to the rights, safety, or welfare of patients (21 CFR 812.3(s)).

---

